### **6.3. DATA MONITORING PLAN**

#### **6.3.1. Monitoring for Side Effects and Adverse Events**

Any infant that develops side effects or minor adverse effects related to the intervention can be continued on study medication at the discretion of the attending physician but the event will be recorded for the trial. If the infant demonstrates tachycardia of 220 beats per minute for greater than 60 minutes, the clinical team should hold the study drug for 24 hours. If tachycardia resolves, the study drug may restart.

Enrolled infants will have their inpatient record reviewed by research coordinators to obtain the following data:

- Infant weight: at birth, day of randomization, and status
- Heart rate: Number of days after randomization until status that there were at least two consecutive heart rates documented over 200 bpm (when infant was not crying) at least 3 hours apart
- Treatment for high blood pressure initiated after randomization until status
- Gastrointestinal issues (NPO for more than 24 hours)
- Use of reflux medications at status

In the largest caffeine trial, the Caffeine for Apnea trial, initial decreased weight gain was reported in the caffeine group as compared to the placebo group but with continued caffeine treatment, long-term weight gain did not differ between caffeine and placebo group infants. Differences in weight gain from the day of randomization, day of discharge (status), and at the infant's well child visits (e.g. one and/or four week periods discharge) will be monitored

Apnea/bradycardia:

The trial will allow for individual study sites to continue their standard practice, and the definition of AoP will be left at the discretion of the neonatology staff treating the infant. If an infant develops apnea, treatment will be left at the discretion of the attending neonatologist or institution. The etiology of the ensuing event and its management (e.g. CPAP, mechanical ventilation, sepsis) will be recorded. Apnea and bradycardia are common in eligible infants even with caffeine treatment and will not be considered serious adverse events.

Other complications of prematurity that are not likely to be related to the intervention will also be collected following randomization into this trial. These include development of necrotizing enterocolitis, intraventricular hemorrhage, periventricular leukomalacia, late onset sepsis, and severe retinopathy of prematurity.

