In addition, the following data will be obtained from the family during follow-up calls and from returned mailed-in forms:

- Infant weights at all health care provider visits (well child and sick visits)
- Reasons for sick visits to the Health Care Provider, urgent care, or emergency room
- Reasons for admission to the hospital
- Final diagnosis when discharged from the hospital

A member of the research staff will be available during the day (8 am to 5 pm) for questions regarding the study medication and trial. If the infant requires medical attention, it should be addressed by the Health Care Provider or emergency medical care staff. The evaluating physician should treat the patient's medical needs, regardless of the involvement in the trial. Once the patient is stable, if the physician or parent/guardian requires further information related to the trial, a member of the research team may be contacted. Information obtained from the trial is unlikely to change the immediate care of the patient if sick.

Expedited serious adverse events will be reported per local IRB guidelines, and to the NICHD and NRN Data Coordinating Center at RTI.

The trial will record side effects and any study related serious adverse events will be reported to the DSMC periodically. Expedited serious adverse events will be reported per local IRB guidelines, and to the NICHD and the NRN Data Coordinating Center at RTI. All protocol deviations and violations will be reported.

The following detail describes the action to be taken for each adverse event below:

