## 3.1.2 Secondary Aims

1. To evaluate the effect of continuing treatment with caffeine citrate in the hospital on number of days to reach physiologic maturity from randomization to discharge up to 48 wks PMA.

- 2. To evaluate the effect of treatment with caffeine until 28 days after hospital discharge on all-cause readmissions to a hospital (including apneic and/or apparent life-threatening events) within the first 8 weeks after discharge by 48 wks PMA.
- 3. To evaluate the effect of treatment with caffeine until 28 days after hospital discharge on the number of all-cause sick visits to urgent care, emergency rooms, or health care provider's office (including apneic and/or apparent life-threatening events) within the first 8 weeks after discharge by 48 wks PMA.
- 4. To evaluate the side effects and adverse events of caffeine continuation in the hospital and after discharge up to 4 weeks post study drug administration.
- 5. To assess the hypothetical cost-savings by the reduction in number of days of hospitalization as a financial benefit of the trial's interventions.

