## 3.2.2 Secondary Outcomes

- 1. The number of days to physiologic maturity after randomization up to 48 wks PMA. Physiologic maturity will be defined as follows:
  - a) Temperature: out of the incubator for at least 48 hours with normal body temperature
  - b) Feeding: oral feeding at a volume of at least 140 ml/kg/day or growing on less than 140 ml/kg/day for at least 48 hours
  - c) Respiratory: apnea-free for at least 5 consecutive days
- 2. Post menstrual age at discharge up to 48 wks PMA, censoring at time of transfer or death (status).
- 3. The number of all cause readmissions, including apneic events and apparent life-threatening events (ALTE), to the hospital within the first four weeks, second four weeks, and first eight weeks combined after discharge from the hospital by 48 wks PMA.
- 4. The number of all cause sick visits to urgent care, emergency room or health care provider office within the first four weeks, second four weeks, and first eight weeks combined after discharge from the hospital by 48 wks PMA.
- 5. Safety outcome measures pre-hospital discharge:
  - a) Weight gain from randomization until status (discharge up to 48 wks PMA, with censoring at time of transfer or death). The weight gain may also be assessed using percentiles including birthweight percentiles.
  - b) The number of days after randomization until status that infant had at least two consecutive heart rates >200 documented at least 3 hours apart (when infant not crying).
  - c) Treatment for high blood pressure initiated after randomization until status.
  - d) The number of episodes between randomization and status that infant was placed NPO for ≥ 24 hours.
  - e) The use of anti-reflux medications started between randomization and status
  - f) The number of days that significant apnea/bradycardia, as defined by documentation of infant receiving any of the following between randomization and status: open label caffeine, other methylxanthines, doxapram, continuous positive airway pressure (CPAP) or ventilatory support for apnea/bradycardia.
  - g) The presence of documented and treated arrhythmias between randomization and status, not due to tachycardia or bradycardia.

h) The onset of documented seizures, as defined by treating with anti-convulsants, between randomization and status.

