#### 6. Death

#### **4 STUDY METHODS**

## 4.1 Overall Study Design and Plan

This study will enroll moderately preterm infants who are between 33% and 35% weeks GA (inclusive) who are being treated with caffeine for AoP and for whom plans are to discontinue caffeine. Once the infant has been screened for eligibility, consented, and the neonatologist has determined that caffeine will be stopped, infants will be eligible to be randomized if they can be started on the study medication within 72 hours after stopping caffeine. They will be randomized either to continuing caffeine citrate at a dose of 10 mg/kg/dose (5 mg/kg caffeine base) given daily (treatment group) or an equal volume of placebo given daily (placebo group), not less than 12 hours between doses, to continue during the hospital stay and for 28 days after hospital discharge. Inhospital dosages will be adjusted weekly based on weight. Post-discharge dosage will be based on weight obtained within 48 hours of discharge.

| Trial Arms            |          | Trial Intervention  |  |
|-----------------------|----------|---|--|
| Intervention
Group | Caffeine | Caffeine citrate 10 mg/kg/day given once daily until 28 days after discharge  |  |
| Control
Group      | Placebo  | Placebo contains all of the excipients except for the active ingredient, caffeine citrate (a volume equivalent to 10 mg/kg of caffeine citrate) given once daily for 28 days after discharge. |  |

The trial medication (caffeine citrate or placebo) will be weight-adjusted on a weekly basis until discharge. An apnea countdown will be done as per local practice before discharge. The duration of this countdown will be site dependent but pre-specified. Many infants may require hospitalization for observation after resolution of the apneas because of other discharge issues such as temperature control or feeding tolerance. If the attending neonatologist decides that re-initiation of open-label caffeine is clinically indicated, caffeine/placebo treatment per randomization will be put on hold until the physician decides to discontinue open label caffeine at which time, the infant will be treated as per randomization within 24-72 hours after open label caffeine is stopped. Infants on study medication who are still in the hospital at 44 weeks PMA will have the caffeine/placebo discontinued.

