## 10.2 Safety Variables

Safety outcome variables are described in the table below.

| Variable   | Туре                       | Definition  |
|--|----------------------------|---|
| Safety Outcomes  |                            |   |
| Weight gain from randomization until status  | Continuous/
Categorical | Change in weight between randomization and in-hospital status. Outcome is censored at 48 weeks PMA and time of transfer or death. May also be assessed using percentiles.   |
| Number of days after
randomization until status
that infant had at least two
consecutive heart rates >200
documented at least 3 hours
apart | Count                      | Number of days between randomization and status with at least 2 consecutive heart rates > 200 bpm at least 3 hours apart. Outcome excludes when infant was crying.  |
| Treatment for high blood pressure initiated after randomization until status   | Categorical                | Presence of treatment for high blood pressure that was started between randomization and status.  |
| Number of episodes between randomization and status that infant was placed NPO for ≥ 24 hours  | Count                      | Number of days between randomization and status in which infant was placed NPO for at least 24 hours  |
| Use of anti-reflux medications between randomization and status  | Categorical                | Presence of use of anti-reflux medication that were started between randomization and status.   |
| Number of days of
significant apnea/bradycardia
between randomization and
status  | Count                      | Number of days between randomization and status with infant showing significant apnea/bradycardia. Significant apnea/bradycardia documented by infant receiving open label caffeine, doxapram, other methylxanthines, CPAP or ventilatory support for apnea/bradycardia |

| Variable  | Type        | Definition   |
|---|-------------|--|
| Presence of documented and treated arrhythmias between randomization and status | Categorical | Presence of treated arrhythmias between randomization and status. Outcome excludes arrhythmias due to tachycardia or bradycardia     |
| Onset of documented seizures between randomization and status                   | Categorical | Presence of documented seizures between randomization and status. Documented seizures are defined by treating with anti-convulsants. |

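### No final-analysis variable in the SAP uses the post-discharge weights, so growth on home caffeine goes unmeasured although the safety aim covers that period

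*SAP*

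**What the plan says.** - **The aim.** SAP 3.1.2, item 4 (and the matching secondary aim in the protocol) sets out to evaluate side effects and adverse events "in the hospital and after discharge up to 4 weeks post study drug administration".
- **The dosing.** SAP 4.1 has study drug given daily, "to continue during the hospital stay and for 28 days after hospital discharge".
- **The safety variables.** SAP 3.2.2 heads its list "Safety outcome measures pre-hospital discharge". Its first item is "Weight gain from randomization until status (discharge up to 48 wks PMA, with censoring at time of transfer or death"), which also defines status. SAP 10.2 turns the list into eight variables with the same end point. Weight is "Change in weight between randomization and in-hospital status"; seizures, for example, are "Presence of documented seizures between randomization and status".
- **The post-discharge weights.** Protocol 6.3.1 obtains from families "Infant weights at all health care provider visits (well child and sick visits"), and says that weight-gain differences, including those "at the infant's well child visits (e.g. one and/or four week periods discharge) will be monitored". SAP 8.3 confirms that the parents' form has room for these weights.
- **Departures from the protocol.** SAP 13 declares none.

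**The concern.** The trial's new element is caffeine given by parents at home. Protocol 3.4 says that evidence on the safety of late-hospital and home methylxanthine treatment is lacking. Protocol 4.5.2 and 6.3.1 both note that the largest earlier caffeine trial saw slower weight gain at first, with no lasting difference. Growth is therefore a side effect that the protocol itself singles out, and home is where it has not been studied.

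As the SAP stands, the final report could conclude on the safety of continued caffeine with a growth comparison that stops on the day home dosing begins. The weights needed to go further are collected, but nothing in the final analysis calls for them.

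**Working it through.** The plan gives no figure to reproduce here. The check sets observation windows side by side and then does arithmetic on the plan's own durations.

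**1. Windows in SAP 10.2.** The rows are weight gain, days with heart rate above 200, blood-pressure treatment, NPO episodes, anti-reflux drugs, days of significant apnea/bradycardia, treated arrhythmia and seizures. Rows ending at status: 8 of 8.

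**2. What in the SAP reaches past discharge, and whether it measures weight.**
- 9.2: all-cause readmissions and sick visits in weeks 1-4, 5-8 and 1-8, and mortality. No weight.
- 10.3 and 10.4: adverse events and serious adverse events summarized by arm, deaths listed; no time limit stated. No weight.
- 7.4: interim safety rule on visits, life-threatening events and hospitalizations related to apnea of prematurity, after eight-week follow-up. Weight enters only through a pointer to section 6.3.1 for other safety outcomes, and only at interim looks.

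So no final-analysis variable uses a weight taken after discharge.

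**3. Share of planned doses given at home.** Inputs: 28 home doses (SAP 4.1); days in hospital after randomization h = 14 on placebo and 12 on caffeine (planning values, SAP 6). Home share = 28/(28 + h).
- Placebo: 28/(28 + 14) = 28/42 = 66.7%
- Caffeine: 28/(28 + 12) = 28/40 = 70.0%

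For other stays: h = 10 gives 28/38 = 73.7%; h = 21 gives 28/49 = 57.1%; h = 28 gives 50.0%; h = 35 gives 28/63 = 44.4%. Home doses are the majority for any in-hospital dosing period under 28 days.

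**4. Share of the aim's window that the 10.2 variables span.** The window is h + 28 days of home dosing + 28 days after the last dose. Share = h/(h + 56).
- Placebo: 14/70 = 20.0%
- Caffeine: 12/68 = 17.6%

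**5. Can the in-hospital weight row stand in?** It ends at discharge, the event that defines the primary outcome. If daily growth were identical in both arms and the stay fell from 14 to 12 days, total gain on caffeine would be 12/14 = 86% of that on placebo, 14% less, from length of stay alone. The row mixes growth with stay and says nothing about growth at home.

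**The case against.** A reader might infer from SAP 10.2 that the trial has no safety analysis after discharge. The documents do not support that. Adverse events, serious adverse events and deaths carry no discharge limit, readmissions and sick visits are analysed to eight weeks, SAP 8.3 calls such visits safety outcomes, and the interim rule rests on post-discharge events.

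A reader might also infer that seizures and arrhythmias at home would go uncompared. That is too strong as well: Protocol 6.3.1 makes both serious adverse events, and SAP 10.3 and 10.4 summarize such events by arm, the serious ones if numbers allow. Only the time window is unstated.

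Third, home growth is not wholly unexamined. The interim safety text sends the data monitoring committee to section 6.3.1, where the post-discharge weights appear, for examination by arm. The protocol's commitment is to monitor weight, not to analyse it as a final endpoint, so the blank entry in SAP 13 is not clearly a misstatement.

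Finally, the pre-discharge list is a stated choice, some items (paired heart rates, NPO episodes) are inpatient chart measures, and SAP 7.7 makes every safety p-value descriptive. The 67% to 70% is also a share of planned doses, not of exposure per kilogram: the home dose is not re-weighted as the infant grows.

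All of this stands, and it narrows the point to one gap. The safety aim is not confined to interim monitoring, and what a committee sees in confidence does not give the published report a growth comparison.

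**Conclusion.** The point holds for growth. All eight SAP 10.2 variables end at status, and the post-discharge weights have no place in the final analysis, although the safety aim runs to four weeks after study drug and about two thirds of planned doses are given at home. It does not extend to post-discharge safety in general. For adverse events, seizures and arrhythmias the only defect is an unstated window.

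The percentages rest on the planning medians of 12 and 14 days and on all 28 home doses being given; missed, held or delayed doses and longer stays move them, as the range above shows. The primary result, sample size and type I error are untouched. This is a worthwhile, inexpensive improvement rather than a flaw that threatens the trial.

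**What to change.** 1. **Add a post-discharge weight row to SAP 10.2.** Compare weight by randomized arm at about one and four weeks after discharge, and in weeks 5-8 where available, from the visit weights already collected. Adjust for weight at randomization, PMA at weighing, center and GA group. Label it descriptive, as SAP 7.7 does for safety comparisons. Say explicitly that it is by randomized arm, because SAP 10.1 evaluates safety by treatment received.
2. **Do not use discharge as the baseline.** Caffeine is hypothesized to bring discharge forward, so age and weight at discharge may differ between arms because of treatment. Weight at randomization avoids this. Visits are timed from discharge, so age at weighing needs its own adjustment.
3. **Prefer well-child weights to sick-visit weights**, since sick visits select unwell infants, and report completeness by arm.
4. **State in SAP 10.3 and 10.4** that the summaries, including seizures and arrhythmias, cover the aim's full window, to four weeks after study drug.

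The cost is one table row, a sentence or two of text and some programming; no new data collection is needed. The downside is data quality: clinic weights will come at irregular times and be incomplete, and the weeks 5-8 window goes beyond the one- and four-week examples in Protocol 6.3.1. The comparison should be read with that in mind.

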### 4.2. SECONDARY OUTCOMES

The secondary outcomes of the study will be:

- a. The number of days to physiologic maturity after randomization up to 48 wks PMA.  
Physiologic maturity will be defined as follows:
  - i. Temperature: out of the incubator for at least 48 hours with normal body temperature
  - ii. Feeding: oral feeding at a volume of at least 140 ml/kg for 48 hours or growing on less than 140 ml/kg/day for at least 48 hours
  - iii. Respiratory: apnea-free for at least 5 consecutive days
- b. Post-menstrual age (PMA) at discharge up to 48 wks PMA, censoring at time of transfer or death (status).
- c. The number of all-cause readmissions, including apneic events and apparent life-threatening events (ALTE), to the hospital within the first four weeks, second four weeks, and first eight weeks combined after discharge from the hospital by 48 wks PMA.  
An apparent life-threatening event is defined by the American Academy of Pediatrics as an event that is perceived by the observer as life-threatening. This event can include apnea, color change (cyanosis), profound change in muscle tone (hypotonia), gagging, and/or choking.
- d. The number of all-cause sick visits, urgent care, emergency rooms, or health care provider's office, within the first four weeks, second four weeks, and first eight weeks combined after discharge from the hospital by 48 wks PMA.
- e. Safety measures pre-hospital discharge
  - a. Weight gain from randomization until status (discharge up to 48 wks PMA, with censoring at time of transfer or death). The weight gain may also be assessed using percentiles including birthweight percentiles.
  - b. The number of days after randomization until status that infant had at least two consecutive heart rates >200 documented at least 3 hours apart (when infant not crying).
  - c. Treatment for high blood pressure initiated after randomization until status.
  - d. The number of episodes between randomization and status that infant was placed NPO for  $\geq 24$  hours.
  - e. The use of anti-reflux medications started between randomization and status
  - f. The number of days that significant apnea/bradycardia, as defined by documentation of infant receiving any of the following between randomization and status: open label caffeine, other methylxanthines, doxapram, CPAP or ventilatory support for apnea/bradycardia.

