Prior to discharge, a research nurse, physician, or pharmacist will educate the parents on storage and administration of the medication to the infant. Other instructions to the parents include preparation of daily dose and if a dose is missed, it may be given at any time on that day if the dose can be given at least 12 hours before the next day's dose is due. If it was not given at all, the parents will be instructed to discard the entire vial that was missed and record it on the medication form. If an infant spits or vomits after a dose is given, another dose should not be given on the same day. Follow-up forms (Medication and Follow up Forms) will be supplied to allow the parents to keep track of daily medication administration and missed doses. The parent will be given a stamped envelope to return the forms to the NRN research coordinator at the end of the 8 weeks. If the study site allows for the use of a gift card, it will be mailed to the parent or guardian when the documents are returned to the research coordinator. The gift card will encourage the family member to return the follow up documents at the end of the 8-week follow up period. Because it will be supplied at the end of the study period, it will have no consequences to the enrollment or treatment of the infant. In addition, the gift card does not constitute payment to the family member for any service provided as part of the trial.

Of note, infants who are deemed to require apnea monitoring at home after enrollment will be allowed its use and this will be noted on a follow-up form. Data from the home monitor recordings will not be used in the trial.

The NRN research coordinator and staff will obtain maternal demographics data including age, race, education, marital status, and parity. In addition, infant data will also be recorded, including weight at birth, randomization, and status; length/head circumference at birth and status; date of status; date of last apnea episode recorded after randomization; use of CPAP or mechanical ventilation; date of last NPO episode lasting >24 hours as well as the number of episodes of NPO >24 hours following randomization; date of last orogastric or nasogastric feed; date of last day in incubator; dates of initiation and termination of open label caffeine therapy; and information related to side effects and adverse events.

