Prior to discharge, a research nurse, physician, or pharmacist will educate the parents on storage and administration of the medication to the infant. Other instructions to the parents include preparation of daily dose and if a dose is missed, it may be given at any time on that day if the dose can be given at least 12 hours before the next day's dose is due. If it was not given at all, the parents will be instructed to discard the entire vial that was missed and record it on the medication form. If an infant spits or vomits after a dose is given, another dose should not be given on the same day. Follow-up forms (Medication and Follow up Forms) will be supplied to allow the parents to keep track of daily medication administration and missed doses. The parent will be given a stamped envelope to return the forms to the NRN research coordinator at the end of the 8 weeks. If the study site allows for the use of a gift card, it will be mailed to the parent or guardian when the documents are returned to the research coordinator. The gift card will encourage the family member to return the follow up documents at the end of the 8-week follow up period. Because it will be supplied at the end of the study period, it will have no consequences to the enrollment or treatment of the infant. In addition, the gift card does not constitute payment to the family member for any service provided as part of the trial.

Of note, infants who are deemed to require apnea monitoring at home after enrollment will be allowed its use and this will be noted on a follow-up form. Data from the home monitor recordings will not be used in the trial.

The NRN research coordinator and staff will obtain maternal demographics data including age, race, education, marital status, and parity. In addition, infant data will also be recorded, including weight at birth, randomization, and status; length/head circumference at birth and status; date of status; date of last apnea episode recorded after randomization; use of CPAP or mechanical ventilation; date of last NPO episode lasting >24 hours as well as the number of episodes of NPO >24 hours following randomization; date of last orogastric or nasogastric feed; date of last day in incubator; dates of initiation and termination of open label caffeine therapy; and information related to side effects and adverse events.

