#### 10 SAFETY ANALYSES

## 10.1 Overview of Safety Analysis Methods

All safety analyses will be performed using all participants who were randomized and evaluated based on the treatment they received. The frequency of toxicities potentially attributable to study treatment will be determined. Treatment and resolution of all safety endpoints will also be documented. Treatment groups will be compared for incidence of events with a chi-squared or Fisher's exact test, and incidence density (events per person-months of exposure) will be calculated.

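### SAP 10.2 names the NPO safety variable as a count of episodes but defines it as a count of days, which is not the outcome stated elsewhere in the protocol and SAP

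*SAP*

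**What the plan says.** **SAP 10.2 Safety Variables.** The row is typed as a count. Its name is "Number of episodes between randomization and status that infant was placed NPO for ≥ 24 hours". Its definition is "Number of days between randomization and status in which infant was placed NPO for at least 24 hours".

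**Outcome statements.** SAP 3.2.2, item 5d, has "The number of episodes between randomization and status that infant was placed NPO for ≥ 24 hours". Protocol 4.2, under the pre-discharge safety measures, begins in the same way, "The number of episodes between randomization and status that infant was placed NPO for", and then gives the 24-hour threshold. The protocol abstract (Section 1, secondary outcome e) also counts episodes.

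**Data listed for collection.** SAP 4.8 lists the "date of last NPO episode lasting >24 hours as well as the number of episodes of NPO >24 hours following randomization". Protocol 5.2.3 lists the same two items.

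**Analysis.** SAP 10.1 compares the incidence of events between groups with a chi-squared or Fisher's exact test and adds that "incidence density (events per person-months of exposure) will be calculated". SAP 7.7 makes p-values for safety parameters descriptive only.

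**Changes from the protocol.** SAP section 13 declares none.

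**The concern.** The definition column is what a programmer would normally implement. Here it carries a different unit from the variable's own name and from every other statement of the outcome. Episodes measure how often feeding was interrupted; days measure for how long. They can rank two groups differently, and a day count can be dominated by one infant with a prolonged interruption. NPO is the gastrointestinal item in the Protocol 6.3.1 monitoring list, so its table should show the quantity the protocol promised. As the row stands, two programmers could reasonably report different numbers from the same records.

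A smaller point sits beside it. The outcome statements admit an episode of exactly 24 hours, whereas the data items ask for episodes longer than that.

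**Working it through.** The plan gives no power, sample size or alpha for this outcome, so there is no figure to reproduce. The check is a comparison of text, followed by a small count.

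**Step 1. Unit and threshold, place by place.**

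| Place | Unit | Threshold |
|---|---|---|
| Protocol Section 1, secondary outcome e | episodes | ≥ 24 h |
| Protocol 4.2 | episodes | ≥ 24 h |
| SAP 3.2.2, item 5d | episodes | ≥ 24 h |
| SAP 10.2, variable name | episodes | ≥ 24 h |
| SAP 10.2, definition | **days** | at least 24 h |
| Protocol 5.2.3, data items | episodes | > 24 h |
| SAP 4.8, data items | episodes | > 24 h |
| Protocol 6.3.1, data from the inpatient record | none stated | more than 24 h |

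Only the SAP 10.2 definition uses days. The same table has two other count rows, for high heart rate and for significant apnea/bradycardia, and both use days in name and definition alike. The NPO row is the only count row that disagrees with itself, which suggests a drafting slip rather than a decision.

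**Step 2. What the definition could yield.** The SAP does not say how a day is counted. The durations and the 10:00 start below are assumptions, since the documents give none. With the start at hour 10 of day 0 and duration D, the episode ends at hour 10 + D.

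- 24-hour periods: D / 24.
- Calendar days touched: an episode of D = 24k hours runs from day 0 to day k, so k + 1.
- Full calendar days: the first and last days are partial, so k − 1.
- Days on which an episode began: 1 for each episode here.

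| NPO history (assumed) | Episodes | 24 h periods | Days touched | Full days | Days an episode began |
|---|---|---|---|---|---|
| One of 24 h (k = 1) | 1 | 1 | 2 | 0 | 1 |
| One of 96 h (k = 4) | 1 | 4 | 5 | 3 | 1 |
| One of 168 h (k = 7) | 1 | 7 | 8 | 6 | 1 |
| Four separate, 24 h each | 4 | 4 | 8 | 0 | 4 |

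On the three ordinary readings of a day count, the 168-hour episode scores 6 to 8 instead of 1.

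**Step 3. Effect on the rate.** Incidence density is the count divided by person-months. For fixed exposure it moves in proportion to the count. Take one group whose only NPO is the 96-hour episode and another, with equal exposure, that has the four 24-hour episodes. The ratio of the second group to the first is:

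- episodes: 4 / 1 = 4;
- 24-hour periods: 4 / 4 = 1;
- days touched: 8 / 5 = 1.6;
- full days: 0 / 3 = 0.

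So the unit, and then the day convention, can change the comparison. This is an illustration of the mechanism, not a forecast.

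**Step 4. Effect on any versus none.** An infant with a qualifying episode normally scores at least 1 in either unit, so the chi-squared or Fisher comparison would normally be the same. The exception in the table is the full-calendar-day reading, where a single 24-hour episode starting at 10:00 scores 0.

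**The case against.** The mismatch itself is plain text within one row, and nothing elsewhere reconciles it. The fair objections concern how much follows from it.

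- **A reader might infer that long episodes will certainly be counted several times.** The documents do not support certainty. The definition can also be read as counting days on which a qualifying NPO placement began, and then a long episode scores 1. That is the less natural reading and the text does not state it, but it is open. The supportable statement is that a long episode may be counted several times.
- **A reader might infer that the data collected cannot supply a day count.** That goes too far. The lists in Protocol 5.2.3 and SAP 4.8 are introduced as inclusive, the data come from the chart, and the In-hospital Outcomes Form (Protocol Section 9) is named but not shown. What stands is that no NPO-day count is listed. If days were in fact unavailable, the programmer would presumably fall back on the episode count, so inflated counts and missing data cannot both be the harm.
- **A reader might infer that the trial's safety conclusions are at risk.** They are not. The formal interim safety rule in SAP 7.4 rests on visits, life-threatening events and hospitalizations related to apnea, and safety p-values are descriptive. SAP 10.1 also words its rate in terms of events, which points towards episodes.
- **The threshold difference is a separate matter.** It affects only an episode of exactly 24 hours.

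All of these limits stand. None removes the need to correct a derivation rule that names one unit and defines another.

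**Conclusion.** The point holds as a minor correction to a variable definition. Followed as written, the SAP 10.2 definition does not produce the protocol's NPO outcome, and no change from the protocol was declared.

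The size depends on durations and a day convention that the documents do not give: under the stated assumptions, 1 episode becomes 6 to 8 days for 168 hours of NPO, and 3 to 5 days for 96 hours. The effect is confined to the count and the incidence density of one descriptive safety outcome. The any-versus-none comparison would normally be unchanged, and the primary outcome, sample size, alpha and formal interim safety bound are untouched.

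**What to change.** 1. Change the definition in SAP 10.2 to the number of separate NPO episodes lasting at least 24 hours between randomization and status. This is one table cell, and it brings the row into line with its own name, SAP 3.2.2 and the protocol.
2. If NPO days are also of interest, add them as a separately named variable, state how a day is counted, and confirm that the form collects what is needed.
3. In the same edit, reconcile the threshold: at least 24 hours in the outcome statements and SAP 10.2, against more than 24 hours in Protocol 5.2.3, Protocol 6.3.1 and SAP 4.8. This touches both documents and calls for a check of how the In-hospital Outcomes Form words the item, so it costs a little more than the unit correction.

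None of this requires a new analysis or a change to the design.
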